#### **4.2.2 Randomization**

Only patients who meet the eligibility criteria (Section 4.1) will be randomized to a treatment arm in this trial. The treatment arms will run in parallel.

Computer-generated randomization lists will be prepared centrally by the Sponsor's Department of Global Biometrics. Patients will be randomized to one of the two treatments in a 1:1 ratio stratified by baseline age group (<75 and ≥75 years of age) and region (North America and Other regions).

The patients will be randomized and allocated to a treatment through the eCRF and thereby receive a unique randomization number. The randomization must be performed at Visit 2 (Month 0).

#### **4.3 Restrictions**

##### **4.3.1 Prior and Concomitant Therapies**

Patients must be treatment-naïve with regard to ADT at time of randomization, except for neoadjuvant/adjuvant ADT given in combination with prostatectomy or radiotherapy with curative intent. This treatment should have been terminated at least 12 months prior to randomization.

Concomitant treatment with anti-androgens (e.g. bicalutamide 50 mg once a day) for a maximum period of up to 28 days is allowed in metastatic patients requiring initial symptomatic flare protection at the discretion of the Investigator. Other hormonal management of prostate cancer is not allowed prior to or during the trial (Section 4.1). However, if a patient develops signs of disease progression, e.g. increased clinical signs and symptoms or rising PSA, additional secondary therapy can be added at the discretion of the Investigator to treat the prostate cancer. Patients on secondary treatments will be handled as described in Section 4.3.2.

The Investigator will be encouraged to treat patients for their pre-existing CVD and any CVD that may be diagnosed during the trial according to standard-of-care. Other medication, which is considered necessary for the patient's safety and well-being, may be given at the discretion of the Investigator.

Details of all concomitant medications, and other therapies including surgical procedures, e.g. revascularizations including the main reason for their prescription must be recorded in the medical source data and the eCRF for all eligible patients at the Screening visit. This information should include name of the drug, route of administration, indication, and duration of treatment. It has to be clearly stated if the medication is given to treat progression of the prostate cancer. Any changes (including new therapies) must be recorded at each subsequent trial visit.

##### **4.3.2 Prohibited Therapy**

Treatment with an investigational drug within the last month prior to randomization or longer is prohibited if considered to possibly influence the outcome of the trial.

The following concomitant medications are prohibited from randomization until the End-of-Trial:

- Surgical castration or other hormonal manipulation in addition to the IMPs
- Anti-androgens for combined androgen blockade (anti-androgen use for initial flare protection is allowed for a maximum period of up to 28 days)
- Estrogens
- Megestrol acetate
- Ketoconazole
- Abiraterone
- Enzalutamide

In case any additional hormonal therapy has been initiated as a combination treatment with the IMP, this is considered a change of ADT regimen and the patient should be called in for an end-of-treatment visit and followed-up as described in Section 4.4.

#### **4.3.3 Other Restrictions**

Patients planning to father a child should not participate in this trial since the risks associated with sperm exposure to degarelix have not been evaluated.

#### **4.4 Withdrawal Criteria**

The patients have the right to withdraw from IMP treatment and/or the trial at any time for any reason without the need to justify their decision.

Withdrawal of consent for treatment should be distinguished from withdrawal of consent for follow-up visits/telephone contacts and from withdrawal of consent for non-patient contact follow-up, e.g., medical records checks. Therefore, when giving written consent for participation in the trial, patients will also be specifically asked to give written consent to safety follow-up procedures that will take place in case of withdrawal from IMP treatment, and/or in case a patient is lost to follow-up.

Patients should be informed that not giving consent, or requesting withdrawal of consent for safety follow-up, will jeopardize the public health value of the trial. Withdrawal of consent for safety follow-up should be accompanied by documentation of the reason for withdrawal.

Patients who withdraw from IMP treatment and/or the trial should be explicitly asked about the contribution of possible adverse events to their decision to withdraw consent, and any adverse event information elicited should be documented.

Preferably the patient should withdraw consent in writing and, if the patient or the patient's representative refuses or is physically unavailable, the trial site personnel should document and sign the reason for the patient's failure to withdraw consent in writing.

A patient who prematurely discontinues treatment with IMP, or receives prohibited medication (Section 4.3.2), should be called in for an end-of-treatment visit (Section 6.5) as soon as possible (within 30 days) after a decision of treatment discontinuation has been taken. The reason for premature IMP discontinuation should be recorded in the eCRF. The patient should then be contacted by telephone each month throughout the trial period for collection of follow-up information on hospitalizations and potential CV events, and concomitant medication. At the telephone follow-ups, information will be collected using the standardized questions regarding hospitalizations and/or ER visits that may have occurred since the last telephone follow-up as described in Section 8.2.3. In case the patient has experienced a potential CV event, related event documentation will need to be collected for evaluation by the CEC Committee. After 336 days of participation in the trial, the patient should be called in for an end-of-trial visit (Section 6.6).

In case a patient is lost to follow-up, despite every attempt (e.g., certified mail, telephone contact of patient or patient relatives) to get in contact, the vital and medical status of the patient should be investigated an additional last time at the end of the trial for that patient (i.e. 12 months after Visit 1), by accessing the patient's hospital records, or publicly available sources such as national registries, newspaper obituaries and social networking websites. Attempts may also be made to contact the patient or his relatives to ascertain this information. However, the patients have the right to withdraw their consent for collection of this information at any time, without the need to justify their decision.a

In case the patient has withdrawn his consent for participation in the trial, including any follow-up activities, no new data can be entered into the eCRF and data are recorded in the medical records only. Correction of previous data entries and/or entering of data related to visits/procedures done prior to but made available after withdrawal of consent (e.g. laboratory results) will be allowed unless the patient disapproves it.

The Investigator also has the right to withdraw patients from the trial or from treatment with IMP. Since an excessive rate of trial withdrawals or IMP treatment withdrawals can render the trial devoid of meaning, the unnecessary withdrawal of patients should be strictly avoided and all necessary measures should be taken to prevent withdrawals/discontinuations from IMP treatment. In case of the occurrence of any CV event, the Investigator will be encouraged to let the patient continue in the trial as per protocol if this is not considered to constitute a safety concern.

---

a **Note:** *In the UK, the following paragraph is applicable instead:*

In case a patient is lost to follow-up, despite every attempt (e.g., certified mail, telephone contact of patient or patient relatives) to get in contact, the vital and medical status of the patient should be investigated an additional last time at the end of the trial for that patient (i.e. 12 months after Visit 1), by accessing the patient's hospital records, or publicly available sources such as national registries and newspaper obituaries. Attempts may also be made to contact the patient or his relatives to ascertain this information. However, the patients have the right to withdraw their consent for collection of this information at any time, without the need to justify their decision.

Reasons for discontinuation from the trial or treatment with IMP include:

- Significant non-compliance to trial protocol, as judged by the Investigator and/or the Sponsor
- Other medical or safety reasons, as judged by the Investigator and/or the Sponsor

Patients discontinued from the trial will not be replaced.

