## **7.2.4 Safety Endpoints**

### **7.2.4.1 Adverse Events**

Adverse events will be recorded from Visit 1 until the End-of-Trial visit. Adverse events that occur before the administration of the first dose of IMP at Visit 2 will be regarded as pre-treatment adverse events. For each adverse event the following parameters are recorded on the Adverse Event Log: description of event, date and time of onset, intensity, causal relation to IMP, action taken to IMP, other actions taken, seriousness of the adverse event, date and time of outcome, and outcome. Definitions are provided in Section 8.1.

Data on suspected CV-related adverse events (except for pre-treatment events) will be delivered to the CEC Committee before the adjudication of MACE takes place (Sections 7.1.1 and 3.4.1). Potential CV-related adverse events will be closely followed.

In case of IMP treatment discontinuation, the patient should be followed for the entire duration of the trial for recording of adverse CV events (Section 4.4).

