### **8.2 Collection and Recording of Adverse Events**

#### **8.2.1 Collection of Adverse Events**

The Investigator must monitor the condition of the patient throughout the trial from the time of obtaining informed consent until the last visit. Adverse events will be recorded from the time point of obtaining signed informed consent until the End-of-Trial visit. Any concomitant illnesses, other than prostate cancer, or any clinically significant signs or symptoms that are present at the Screening visit (Visit 1) will be recorded as medical history (Section 7.3.3). Adverse events that occur before administration of the first dose of IMP at Visit 2 will be regarded as pre-treatment adverse events.

The sources of adverse events cover:

- The patient's response to general questions about his health (a standard non-leading question such as "How have you been feeling since your last visit?" is asked at each visit)
- Symptoms spontaneously reported by the patient
- Investigations and examinations where the findings are assessed by the Investigator to be clinically significant changes or abnormalities
- Other information relating to the patient's health becoming known to the Investigator

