### 8.2.3 Cardiovascular-Related Adverse Events

The objective and scope of the present trial is to investigate the short-term risk of CV events in patients with pre-existing CVD. Thus, CV-related adverse events and any worsening in CV status will be recorded from Visit 2 until the End-of-Trial visit and will be captured separately in the eCRF.

At each monthly visit/contact with the patient, the Investigator must obtain information about:

- Admission to hospital or ER since last visit
- Death
- Admission for chest pain (ischemic) symptoms that could be an unstable angina or myocardial infarction event
- Admission for new neurological symptoms that could be a cerebrovascular (stroke) event
- Any drawn creatinine kinase (CK), creatine kinase-muscle brain (subunit) (CK-MBs) or troponin samples since last visit

The information obtained should be entered in the eCRF. In case pre-defined items on the eCRF checklist are answered affirmatively, a specific clinical endpoint form in the eCRF relating to each of the questions that were answered “yes”, must be completed by the site personnel.

The following questions should be addressed directly to patients when reviewing this checklist at every monthly visit/contact:

Were you admitted to the hospital or visited the emergency department since your last visit/contact with us?

- If you were admitted to the hospital or visited the emergency department, was it due to symptoms such as chest pain (feeling of tightness, heavy pressure, squeezing or crushing pain), shortness of breath, nausea, fatigue, dizziness, or profuse sweating? These symptoms may have occurred at rest or during exercise.
- If you were admitted to the hospital or visited the emergency department, was it due to symptoms such as sudden onset of weakness or difficulty in coordinating muscles needed to speak (slurred speech), difficulty swallowing, visual impairment (you could not see well), or numbness or weakness of legs or arms (you could not properly lift or move your arms or legs)?
- If you were admitted to the hospital or visited the emergency department do you recall if the physician who treated you collected your blood to check if your heart muscle was damaged?

Data on potential CV-related adverse events will be delivered to the CEC Committee before the adjudication of MACEs take place (Sections 3.4.1 and 7.1.1). Potential CV-related adverse events will be closely followed.

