#### 9.8.2 Adverse Events

Adverse events will be tabulated by SOC and preferred term using MedDRA version 17.1 or later. The total number of patients reporting an adverse event, the percentage of patients (%) with an adverse event, and the number of events (E) reported will be presented. Adverse events will be

classified according to their intensity (using CTCAE version 4.02) and relationship to the IMP by the Investigator.

Adverse events will be regarded as 'pre-treatment' if they occur between screening and the initial injections with IMP. Adverse events which occur in the time interval from initial dosing to 3 months after (1 month=28 days) last dosing of IMP will be considered to be 'treatment-emergent'. Adverse events will be regarded as 'post-treatment' if they occur 3 months (1 month=28 days) or more after the last dosing of IMP.

Written narratives will be issued for all serious adverse events and adverse events leading to withdrawal. Missing values will be treated as missing, except for causality of adverse events to trial drug. If causality is missing, the adverse event will be regarded as being reasonably possibly related to IMP. Related adverse events (judged as being reasonably possibly related to trial drug) will be termed adverse drug reactions (ADRs).

An adverse event overview summary table will be prepared for the safety analysis set. It will display the number of patients reporting an adverse event, the percentage of patients (%) with an adverse event and the number of events reported for each treatment group. The following categories will be displayed:

- All adverse events
- Deaths
- SAEs
- Severe adverse events (CTCAE grade 3-5)
- Adverse events leading to withdrawal
- ADRs

Summary tables will be prepared for the incidence of treatment-emergent adverse events by MedDRA SOC (alphabetically) and preferred term (in decreasing frequency of occurrence). The tables will display the total number (N) of patients exposed, and the percentage of patients (%) reporting treatment-emergent adverse events. Summary tables will be prepared for:

- All adverse events
- Common adverse events (at least 5% of patients)
- Adverse events by causality (related/unrelated)
- Adverse events by intensity
- ADRs by intensity
- SAEs
- Adverse events leading to withdrawal

Supporting data listings will be provided for:

- Adverse events sorted by trial site/Investigator/patient number
- Adverse events sorted by MedDRA SOC and preferred term
- SAEs

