10.2.1 Overview of Treatment-Emergent Adverse Events

Adverse events will be regarded as 'pre-treatment' if they occur between screening and the initial injections with IMP. Adverse events which occur in the time interval from initial dosing to 3 months after (1 month=28 days) last dosing of IMP will be considered to be 'treatment-emergent'. Adverse events will be regarded as 'post-treatment' if they occur 3 months (1 month=28 days) or more after the last dosing of IMP.

An adverse event overview summary table will be prepared including the number of patients reporting an adverse event, the percentage of patients (%) with an adverse event, and the number of events (E) reported, for the following categories:

- Treatment-emergent adverse events
- Deaths
- Serious adverse events
- Adverse events leading to withdrawal
- Severe and life threatening adverse events
- Adverse drug reactions

TLF Table: Overall summary of treatment-emergent adverse events – Safety

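### After trial drug is stopped early, the scripted monthly calls carry no open adverse-event question, so new non-hospitalised, non-CV events in the 84-day treatment-emergent window risk under-ascertainment

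*Protocol*

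**What the plan says.** **What must be recorded.** Protocol 8.2.1: "Adverse events will be recorded from the time point of obtaining signed informed consent until the End-of-Trial visit". It makes no exception for patients off trial drug. The standard non-leading question about how the patient has been "is asked at each visit"; telephone contacts are not named.

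**What the calls contain.** After an early stop, Protocol 4.4 (and the synopsis) has the patient "contacted by telephone each month throughout the trial period for collection of follow-up information on hospitalizations and potential CV events, and concomitant medication". On the call, "information will be collected using the standardized questions regarding hospitalizations and/or ER visits that may have occurred since the last telephone follow-up", with a reference to 8.2.3. That checklist opens with "Were you admitted to the hospital or visited the emergency department since your last visit/contact with us", and its three symptom and blood-test questions all depend on a yes. For patients who discontinue, 7.2.4.1 adds that "the patient should be followed for the entire duration of the trial for recording of adverse CV events".

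**What is counted.** SAP 10.2.1 classes as treatment-emergent "Adverse events which occur in the time interval from initial dosing to 3 months after (1 month=28 days) last dosing of IMP". Protocol 9.8.2 sets the same limit.

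**The concern.** The incidence and intensity of adverse events is a named safety endpoint. While on drug, a patient meets the open question every month. After the End-of-Treatment visit, a site that follows 4.4 literally does not ask it again until Day 336, although part of the treatment-emergent window may still be running. The side effects that Protocol 1.3 lists for these drugs, such as hot flashes, joint pain, fatigue and impotence, seldom lead to a hospital or emergency visit, so the scripted questions are poorly suited to finding them.

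Two features add to this:

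- The part of the window left after the End-of-Treatment visit depends on where in the dosing cycle the patient stops. The cycle is 28 days for degarelix and 84 for leuprolide, so ascertainment may differ by arm.
- Under SAP 10.2, a missing onset date is set to the first day of dosing. An event recalled late and without a date is therefore counted as treatment-emergent, whenever it occurred.

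**Working it through.** **1. The plan's window.** 3 months × 28 days = 84 days after the last dose, in both arms (Protocol 9.8.2, SAP 10.2.1).

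**2. Contacts after a decision to stop.**

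| Contact | Timing | Adverse-event content |
|---|---|---|
| End-of-Treatment visit (4.4, 6.5) | within 30 days of the decision | all adverse events |
| Monthly calls (4.4, 8.2.3) | until Day 336 | hospital/ER questions, possible CV events, medication |
| End-of-Trial visit (6.6) | Day 336 | all adverse events |

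The uncovered part of the window therefore starts at the End-of-Treatment visit and ends at day 84 after the last dose.

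**3. Single patients.**

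- Degarelix, last dose Day 140, decision at the Day 168 visit. End-of-Treatment visit: Day 168 to 198. Window end: 140 + 84 = Day 224. Uncovered: 224 − 198 = 26 to 224 − 168 = 56 days, or 31% to 67% of 84.
- Leuprolide, last dose Day 84, decision when the next dose is due on Day 168. Window end: 84 + 84 = Day 168. Uncovered: 0 days.
- Leuprolide, decision 28 days after a dose: 26 to 56 days, the same as the degarelix patient.

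**4. Averages under stated assumptions.** Let d be the days from last dose to decision and L the days from decision to End-of-Treatment visit. Uncovered days are U = max(0, 84 − d − L). Assume d is uniform over one dosing interval (0–28 days for degarelix, 0–84 for leuprolide; intervals from Protocol 3.5.5) and L is 0, 15 or 30.

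- Degarelix: d + L is at most 58, so mean U = 84 − 14 − L.
- Leuprolide: mean U = (84 − L)² / (2 × 84), and the share with U = 0 is L/84.

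| L (days) | Degarelix mean U | Leuprolide mean U | Leuprolide, whole window before the visit |
|---|---|---|---|
| 0 | 70 | 84²/168 = 42 | 0% |
| 15 | 55 | 69²/168 = 28 | 15/84 = 18% |
| 30 | 40 | 54²/168 = 17 | 30/84 = 36% |

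U ranges from 26 to 84 days for degarelix, where no patient has the whole window covered, and from 0 to 84 for leuprolide.

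**5. Limit of the formula.** It applies when the window closes by Day 336, that is, for a last dose by Day 336 − 84 = 252. After a later dose the End-of-Trial visit falls inside the window and shortens the gap. Only degarelix has scheduled doses after Day 252, so the difference between arms is smaller for late stops.

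**The case against.** The case for leaving the plan alone has four parts.

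- **The duty already exists.** 8.2.1 covers every patient to the End-of-Trial visit. 7.2.4.1 opens with the same rule, and its later sentence on CV events does not say that nothing else is recorded. This stands. The documents do not exclude other adverse events; 4.4 and 7.2.4.1 fail to carry the duty into the calls.
- **There are other routes.** Calls collect medication, and under 8.1 the reason for a medication change or a medical consultation is an adverse event. Unscheduled visits are possible (6.7). On-site review looks at symptoms, medication changes and specialist visits (11.2), although its stated aim is to find suspected MACEs. Patients who withdraw are asked whether adverse events contributed (4.4), and known events are followed until resolved or stable (8.4.1). A reader might infer that a non-hospitalised event can come to light only by spontaneous report or final recall. These sections do not support that. What remains exposed is mainly new-onset, untreated, non-hospitalised, non-CV events.
- **The period is asked about in the end.** The End-of-Trial visit records adverse events for patients off drug too. This also stands: the weakness is late recall, not the absence of any question. In the degarelix example the delay after the End-of-Treatment visit is 336 − 198 = 138 to 336 − 168 = 168 days.
- **A CV focus is defensible.** The trial was set up to measure CV risk. That is a fair reason for a short call, but it does not explain why 8.2.1 and the 84-day window were left unchanged for these patients.

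**Conclusion.** The concern holds as a gap in alignment with a real but unmeasured consequence. In patients who stop early, new non-hospitalised, non-CV adverse events between the End-of-Treatment visit and day 84 after the last dose have no scheduled open question until the End-of-Trial visit. They are at risk of under-ascertainment.

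The mean uncovered time is about 70/55/40 days for degarelix and 42/28/17 for leuprolide. These figures rest on uniform stop times and assumed visit lags of 0/15/30 days, neither of which is given in the documents.

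A reader might infer from them that the adverse-event tables favour degarelix. The documents do not support that step. No rate of stopping trial drug is given (the 5% in the SAP's sample-size section is a drop-out assumption), and a leuprolide patient who stops early in the cycle has the same gap as a degarelix patient. A difference between arms is possible; neither its size nor the number of events lost can be estimated.

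The MACE endpoints are not affected. The calls ask about hospital contact and possible CV events, and the primary analysis censors at treatment discontinuation.

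**What to change.** - In Protocol 4.4 and the synopsis, add the non-leading question already used at visits to the monthly calls, at least until day 84 after the last dose and preferably to the End-of-Trial visit, as 8.2.1 already requires.
- In 7.2.4.1, widen the wording on follow-up after discontinuation from adverse CV events to adverse events, including CV events.
- SAP Section 3 reports that the trial was terminated early with 545 patients randomized. Where the calls are already complete, a new script cannot recover the data. State instead in SAP 10.2.1 that adverse events after the End-of-Treatment visit were ascertained less intensively, and tabulate them separately by arm.

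The cost is protocol wording, a few minutes on calls that already take place, and some more adverse-event records. The SAP alternative costs one sentence and one table. Neither touches treatment.
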